4.2.1.4 Handling of Missing Data

No imputation is planned for missing endpoint values.

4.2.1.5 Primary Analysis of Primary Immunogenicity Endpoint

For the Day 29 primary analysis model-adjusted GMCs, along with their corresponding 95% CIs, will be estimated using an analysis of covariance (ANCOVA) model that includes a continuous dependent variable of log 2 response at Day 29, study group as a fixed effect (factor), and log 2 baseline response (continuous) and age group (categorical; 60 to 69, 70 to 79, and ≥ 80 years of age) as covariates.

Least square means and 95% CIs will be back-transformed to provide Day 29 model-adjusted GMCs and CIs for each study arm.

The following plots will be created for the Day 29 analysis:

- A bar plot by study group showing the GMCs and 95% CIs at baseline (raw values) and Day 29 (adjusted values)
- A line plot by study group showing the GMCs and 95% CIs at baseline (raw values) and Day 29 (adjusted values)
- A boxplot with scatterplot overlay by study group showing the distribution of the raw concentration data at Day 29
- A reverse cumulative distribution plot of the fold rise at Day 29, with fold rise values displayed on the x-axis and the percentage of participants with fold rise values greater than or equal to the corresponding fold rise displayed on the y-axis

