Only descriptive statistics will be used to summarize the immunogenicity and safety endpoints. There will be no formal hypothesis testing.

The immunogenicity analysis set will include all randomized and dosed participants in the safety analysis set who had no protocol deviations judged to potentially interfere with the generation or interpretation of an immune response. The safety analysis set will include all randomized and dosed participants. Analyses conducted using these analysis sets will be based on the actual study intervention received.

The sample size of 140 participants is based on having sufficient precision for a descriptive assessment of immunogenicity and safety.

The Day 29 primary analysis will be conducted when all participants have completed their Day 29 visit. Subsequently, the final analysis will be performed when all participants complete the study. For the Day 29 primary analysis, adjusted GMTs and GMT ratios, along with their corresponding 95% CIs, will be estimated using an ANCOVA model that includes a dependent variable of log titers, study arm as a fixed effect, and log baseline titer and age group as covariates. For the final analysis, model-adjusted GMTs and GMT ratios at Days 29 and 181, along with their corresponding 95% CIs, will be estimated using an MMRM that includes a dependent variable of log titers, study arm as a fixed effect, log baseline titer, age group (60 to 69, 70 to 79, and ≥ 80 years of age), visit indicators (Days 29 and 181) as covariates, and a study arm by visit interaction term.

[figure not shown]
Model-adjusted GMT and GMT ratios will be used for analyses of the nAb response endpoints. Geometric mean fold rises and seroresponse (defined as a GMFR ≥ 4) will be unadjusted.

Model-adjusted GMT and GMT ratios, along with their corresponding 95% CIs, will be calculated for each study arm and will be summarized by visit based on the immunogenicity analysis set. Unadjusted GMFR and seroresponse, along with their corresponding 95% CIs will be calculated for each study arm and summarized by visit.

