9.4.2 Immunogenicity

9.4.2.1 Primary and Secondary Endpoint(s)

Geometric mean titer (GMT) will be calculated as the anti-logarithm $\Sigma(\log_2 \text{transformed titer})/n$, ie, as the anti-logarithm transformation of the mean of the log-transformed titer, where n is the number of participants with titer information. The 95% CI about the GMT will be calculated as the anti-logarithm transformation of the upper and lower limits for a two-sided CI for the mean of the log-transformed titers.

The fold rise is calculated as the ratio of the post-dose titer level to the pre-dose titer level.

Geometric mean fold rise (GMFR) will be calculated as anti-logarithm of $\Sigma(\log_2$ transformed (post-dose titer/ pre-dose titer)/n. The 95% CIs for GMFR will be calculated similarly to those for GMT.

Seroresponse is a binary outcome where a success is when the fold rise in titers compared to baseline is ≥ 4 . The number and percentage of participants with post-vaccination seroresponse, and 95% CIs, calculated using the Clopper-Pearson exact method, will be provided. In the event of a 0% or 100% seroresponse, a one-sided 97.5% CI will be reported.

For the Day 29 primary analysis, adjusted GMTs and GMT ratios, along with their corresponding 95% CIs, will be estimated using an analysis of covariance (ANCOVA) model that includes a dependent variable of log titers, study arm as a fixed effect, and log baseline titer and age group as covariates. For the final analysis, model-adjusted GMTs and GMT ratios at Days 29 and 181, along with their corresponding 95% CIs, will be estimated using an mixed model for repeated measures (MMRM) that includes a dependent variable of log titers, study arm as a fixed effect, log baseline titer, age group (60 to 69, 70 to 79, and ≥ 80 years of age), visit indicators (Days 29 and 181) as covariates, and a study arm by visit interaction term.

Model-adjusted GMTs and GMT ratios will be used for analyses of the nAb response endpoints, while raw unadjusted values will be summarized as supportive analyses. GMFR and seroresponse will be unadjusted.

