The unadjusted and model-adjusted GMTs and GMT ratios, along with their corresponding 95% CIs will be calculated for each study arm and summarized by visit based on the immunogenicity analysis set. The unadjusted GMFR and seroresponse along with their corresponding 95% CIs, will be calculated for each study arm and summarized by visit. Descriptive statistics will include number of participants, geometric mean, 95% CI, minimum and maximum. Summaries may be repeated by pre-specified subgroups, including, but not limited to: age group. The final list of subgroup variables will be provided in the SAP.

Primary immunogenicity analyses will be conducted on data reported from samples analyzed by the GFP RSV A neutralization assay conducted at [REDACTED].

Supportive analyses will be performed on results reported by other exploratory assays, with more details provided in the SAP.

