4.2 Endpoint Analyses

The following table section covers details related to the primary and exploratory endpoint analyses.

Table 4. Primary and exploratory estimands

Statistical category	Endpoint	Population	Intercurrent event strategy	Population level summary (analysis)	Details in section
Objective 1: To characterize the nAb responses to RSV A in serum following vaccination with IVX-A12 or licensed RSV vaccine					
Primary Analysis of the Immunogenicity Endpoint	RSV A (GFP MN RSV A Assay, [REDACTED] nAb concentrations at Day 29)	Immunogenicity analysis set	Participant follow-up will be censored at the date of intercurrent event (IPD that may impact immune response, infection with RSV/hMPV, early withdrawal, death)	Model-adjusted GMCs by vaccination group 
 Unadjusted GMCs/GMFRs from baseline by vaccination group Proportion of participants with seroresponse (GMFR ≥ 4 from baseline) by vaccination group. 	4.2.1.5 4.2.1.7
Objective 2: To assess the safety of single IM vaccination with IVX-A12 or licensed RSV vaccine					
Primary Analysis of the Safety Endpoint	Immediate unsolicited AEs within 30 minutes of dosing	Safety analysis set	N/A	Incidence by vaccination group (descriptive)	4.6
	Injection site and systemic solicited ARs through 7 days post-vaccination (Day 1 to Day 8)		N/A	Incidence by vaccination group (descriptive)	4.6
	Unsolicited AEs through 28 days post-vaccination (Day 1 to Day 29)		N/A	Incidence by vaccination group (descriptive)	4.6
	SAEs, MAAEs, and AESIs through 6 months post-vaccination (Day 1 to Day 181)		N/A	Incidence by vaccination group (descriptive)	4.6
Objective 3: To characterize the durability of the nAb responses to RSV A in serum following vaccination with IVX-A12 or licensed RSV vaccine					
Exploratory	RSV A nAb concentrations through Day 181	Immunogenicity analysis set	Participant follow-up will be censored at the date of intercurrent event (IPD)	
 Model-adjusted GMCs by vaccination group and visit 	4.2.3

Statistical category	Endpoint	Population	Intercurrent event strategy	Population level summary (analysis)	Details in section
			that may impact immune response, infection with RSV/hMPV, early withdrawal, death)	
 Unadjusted GMCs/GMFRs from baseline by vaccination group and visit Seroresponse rate by vaccination group and visit 	

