Objective 4: To compare the nAb responses to RSV in serum following vaccination with IVX-A12 or licensed RSV vaccine					
Exploratory	RSV A nAb concentrations through Day 181	Immunogenicity analysis set	Participant follow-up will be censored at the date of intercurrent event (IPD that may impact immune response, infection with RSV/hMPV, early withdrawal, death)	
 Model-adjusted GMCs by vaccination group and visit Model-adjusted GMC ratios by visit Unadjusted GMCs /GMFRs from baseline by vaccination group and visit Seroresponse rate by vaccination group by post-baseline visit Difference in seroresponse rate by post-baseline visit 	4.2.3
Exploratory	RSV B nAb concentrations through Day 181				
Objective 5: To compare the nAb responses to hMPV in serum following vaccination with IVX-A12 or licensed RSV vaccine					
Exploratory	hMPV A nAb titers through Day 181	Immunogenicity analysis set	Participant follow-up will be censored at the date of intercurrent event (IPD that may impact immune response, infection with RSV/hMPV, early withdrawal, death)	
 Model-adjusted GMTs by vaccination group and visit Model-adjusted GMT ratios by visit Unadjusted GMTs/GMFRs from baseline by vaccination group and visit Seroresponse rate by vaccination group and post-baseline visit 	4.2.3
Exploratory	hMPV B nAb titers through Day 181				

Statistical category	Endpoint	Population	Intercurrent event strategy	Population level summary (analysis)	Details in section
				
• Difference in seroresponse rate by post-baseline visit	

4.2.1 Primary Immunogenicity Endpoint – RSV A Neutralizing Antibody Response at Day 29

The primary immunogenicity objective of the study is to characterize the nAb responses to RSV A in serum following vaccination with IVX-A12 or AREXVY.

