4.2.3.2 Exploratory analyses of the exploratory endpoints

To evaluate durability of nAb responses post-vaccination, model-adjusted GMCs/GMTs at Days 29 and 181, along with their corresponding 95% CIs, will be estimated using a mixed model for repeated measures (MMRM) that includes a dependent variable of log 2 responses, study group as a fixed effect, log 2 baseline response, age group, visit indicators (Days 29 and 181) as covariates, and a study group by visit interaction term. An appropriate covariance matrix structure will be selected to address repeated measurements. Least square means and 95% CIs will be back-transformed to provide model-adjusted GMC/GMTs and confidence intervals by study group, for each follow-up visit, Days 29 and 181. Unadjusted GMCs/GMTs, GMFRs from baseline, and seroresponse rate, with corresponding 95% CIs, will be estimated for each study group and summarized by post-baseline visit. Plots described in Section 4.2.1.5 may be repeated for these analyses.

Multiple imputation techniques will not be applied for any missing post-baseline immunogenicity measurement. This is because the MMRM inherently accounts for the missingness, under the assumption that the missing data are missing at random (MAR). Thus considering that missing data are MAR is a reasonable assumption for this descriptive clinical trial, then it is not necessary to perform MI.

To compare nAb response between IVX-A12 and the AREXVY, the GMC/GMT ratio and difference in seroresponse rate, along with corresponding 95% CIs, will be estimated and summarized at Day 29 and Day 181. The difference in seroresponse rate will be unadjusted and the 95% CIs calculated based on the Miettinen-Nurminen method (Miettinen and Nurminen 1985). Unadjusted and model-adjusted (from MMRM above) GMTRs with 95% CIs will be calculated.

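### Does leaving the ANCOVA-adjusted Day 29 ratio out of SAP 4.2.1.5 leave the primary analysis without its between-group comparison?

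*SAP*

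**What the plan says.** **Protocol.** Section 9.4.2.1 attaches the ratio to the ANCOVA: "For the Day 29 primary analysis, adjusted GMTs and GMT ratios, along with their corresponding 95% CIs" are to come from a model with study arm, log baseline titer and age group. The two-visit model belongs to the end of the study: "For the final analysis, model-adjusted GMTs and GMT ratios at Days 29 and 181" (Synopsis; 9.4.2.1 agrees). Model-adjusted values lead, "while raw unadjusted values will be summarized as supportive analyses", and both kinds of ratio are planned: "The unadjusted and model-adjusted GMTs and GMT ratios, along with their corresponding 95% CIs will be calculated for each study arm". The primary estimand, in the synopsis and in Table 2, lists only geometric mean titers and fold rises by group. Comparing RSV responses between vaccines is a separate, exploratory objective in Table 2.

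**SAP.** Section 4.2.1.5 fits the same ANCOVA and states its output as "Least square means and 95% CIs will be back-transformed to provide Day 29 model-adjusted GMCs and CIs for each study arm". Table 4 lists "Model-adjusted GMCs by vaccination group" under Objective 1 and no ratio. Objective 4, exploratory, has "Model-adjusted GMC ratios by visit", with details in 4.2.3. Section 4.2.3.2 says: "Unadjusted and model-adjusted (from MMRM above) GMTRs with 95% CIs will be calculated". Section 3.4.1 defines the ratio as IVX-A12 over AREXVY and takes its CI by back-transforming the interval for a difference of log2 means. Section 2 declares only the change to the immunogenicity analysis set.

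**The concern.** A reader who checks the SAP against protocol 9.4.2.1 finds that an estimate assigned to the primary analysis is absent from the SAP's section on that analysis. The one adjusted ratio with a named source comes from a model containing a Day 181 term, and Day 181 data will not be complete when the primary analysis runs (SAP 3.2). Read literally, the Day 29 report might carry no adjusted ratio, or one from a model the protocol reserves for the final analysis.

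The per-group adjusted means do not fill the gap by themselves. Dividing them gives the point ratio, but its CI needs the standard error of the difference in least square means. Protocol 4.2 says the study should help refine Phase 3 assumptions, so it is fair to ask whether the model behind this contrast is fixed in advance.

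**Working it through.** **1. The plan's own figure.** SAP 3.1 gives a 95% CI of 0.57 to 1.42 for a ratio of 0.9 with 140 participants. The SD is blacked out, so it is solved from the interval using SD = [ln(upper/lower)/2] / [t × √(2/70)], with t = 1.977 (138 df) and √(2/70) = 0.169:

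- From 0.57 to 1.42: 0.456 / 0.334 = 1.366 on the natural-log scale.
- From 0.63 to 1.58 (ratio 1.0): 0.460 / 0.334 = 1.376.

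With SD 1.37, 0.9 × exp(±1.977 × 1.37 × 0.169) gives 0.57 to 1.42. The formula contains no baseline correlation, so the stated precision is that of an unadjusted ratio. Nothing in the sizing depends on where the adjusted ratio comes from.

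**2. Which model can give the adjusted ratio at the primary analysis?** Take the model in SAP 4.2.3.2: group, log2 baseline, age group, visit, and group by visit. Fit it to Day 29 results only.

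- Visit takes one value, so its term merges with the intercept.
- Group by visit merges with group.
- Each participant has one outcome, so the within-person covariance matrix becomes a single variance.

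What remains is log2 Day 29 response = intercept + group + log2 baseline + two age terms + error. These are the five parameters of the ANCOVA in 4.2.1.5, with 140 − 5 = 135 residual df if everyone is evaluable. The group coefficient, its standard error and the back-transformed ratio and CI are identical. The two routes cannot disagree on these data.

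**3. Is anything about the contrast left open?** Outcome, transformation, covariates and evaluable participants are fixed in 4.2.1.1, 4.2.1.2 and 4.2.1.5. Direction and back-transformation are fixed in 3.4.1. The adjusted ratio is 2 raised to the difference in least square means, and the CI limits transform the same way. No analyst choice remains.

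**4. Primary and final analyses side by side.**

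| | Protocol | SAP | Conflict in result |
|---|---|---|---|
| Day 29 ratio, primary analysis | ANCOVA | repeated-measures model, which on Day 29 data is the ANCOVA | none |
| Day 29 and Day 181 ratios, final analysis | repeated-measures model | repeated-measures model | none |

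**5. The two models with Day 181 data present.** Here they can differ at Day 29, because the repeated-measures model has one baseline effect for both visits. Trials of 140 participants were simulated with the SD of 1.37, a Day 29/Day 181 correlation of 0.8 and baseline correlations of 0.3 to 0.8 (correlations assumed, since the documents give none). The central 95% range of the quotient of the two Day 29 ratios was about 0.99 to 1.01 with complete data and equal baseline correlations. At its widest it was 0.92 to 1.10. Mean CI half-widths agreed within 2%. This is the final-analysis setting, where the protocol itself prescribes the repeated-measures model, so these figures do not measure a departure from the protocol.

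**The case for a change.** The strongest case for a change is that the protocol's wording is explicit, Section 2 is where departures are declared, and one sentence in 4.2.1.5 would remove the doubt. Protocol 9.4.2.1 does name ratios for the Day 29 ANCOVA, SAP 4.2.1.5 does omit them, and Section 2 is silent. All of that stands as a matter of wording.

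Two things weaken it. First, the tension lies partly inside the protocol, whose primary estimand has no ratio; SAP Table 4 follows the estimand table, and SAP 3.1 calls the ratio exploratory. Second, the ratio is moved, not dropped: 4.2.3.2 plans it at Day 29, adjusted and unadjusted, with CIs.

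A narrower objection is that some Day 181 results might be in hand at the primary analysis, so that a literal two-visit fit would not reduce exactly to the ANCOVA. Ignoring laboratory time, the earliest Day 181 visit falls on study day 167, so this needs enrolment spread over at least 167 − 29 = 138 days. The documents give no enrolment period, so it cannot be excluded. Even then, SAP 3.4 limits Day 29 summaries to participants with baseline and Day 29 results, and the protocol assigns the ANCOVA to that report. An analyst holding both documents would use the ANCOVA contrast.

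The point does not become a defect for RSV B or hMPV. Those endpoints are exploratory, protocol 9.4.2.2 leaves their analysis to the SAP, and the reduction in step 2 applies to them too.

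**Conclusion.** The mismatch in wording is genuine, but it is a gap that analysts fill correctly from the two documents together. On Day 29 data alone, the adjusted ratio and its CI are the same whether taken from 4.2.1.5 or 4.2.3.2, so the numerical effect is zero. At the final analysis the documents agree. If early Day 181 results entered the fit, the simulations above suggest a difference of at most about 10% either way in 95% of trials, under assumed correlations and with Day 181 data complete or nearly so. Partial Day 181 data were not simulated. For scale, the planned interval extends by a factor of 1.42/0.9 = 1.58 each way.

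The study is descriptive, with no hypothesis test and no multiplicity adjustment, and its sample size was not formally calculated. Restating the contrast would alter no estimate or conclusion. No change to the plan follows. This rests on the primary analysis using Day 29 results, as SAP 3.2 and 3.4 indicate, and on the protocol's statement of the ANCOVA ratio continuing to apply, since the SAP does not withdraw it.

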4 STUDY DESIGN

4.1 Overall Design

This Phase 2 clinical study is a randomized, modified double-blind, active controlled study to characterize the safety and immunogenicity of IVX-A12.

Approximately 140 participants will be randomized in a 1:1 ratio to receive IVX-A12

(approximately N=70) or licensed RSV vaccine, AREXVY (approximately N=70).

Randomization will be centrally stratified by age (60 to 69, 70 to 79, and ≥ 80 years of age).

The Schedule of Activities (SoA) is presented in [Section 1.3](#). Blood will be taken for immunological assessments as per the SoA. All participants will be given a thermometer, ruler, and a proprietary eDiary application designed for use with the participant's smart device or a provisioned eDiary device with instructions for use. Participants will be asked to report on solicited ARs in the eDiary beginning on the day of vaccination (Day 1) and for 7 days following the day of vaccination (up to Day 8). Unsolicited AEs will be collected by participants through Visit 3. SAEs, MAAEs, and AESIs will be recorded throughout the study.

The duration of each participant's involvement in the study will be approximately 6 months following administration of study vaccination.

The study is planned to be conducted at approximately 4-5 sites in the US.

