6.3 Assignment to Study Intervention

All participants will be centrally assigned to randomized study intervention using an Interactive Response Technology (IRT)/ Randomization and Trial Supply Management (RTSM). Randomization will be centrally stratified by age (60 to 69, 70 to 79, and \geq 80 years

of age). Before the study is initiated, the telephone number and call-in directions for the IRT and/or the log in information and directions for the RTSM will be provided to each site.

Study intervention will be dispensed at the study visits summarized in the SoA ([Section 1.3](#)). Returned study intervention should not be re-dispensed to the participants.

The IRT/RTSM will provide to the Investigator(s) or pharmacists the kit identification number to be allocated to the participant at the dispensing visit. Routines for this will be described in the IRT/RTSM user manual that will be provided to each center.

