3.3 Analysis Populations

The following populations are defined (Table 2):

Table 2 Populations for Analysis

Population/analysis set	Description
Safety analysis set (SAF)	All randomized participants who receive study intervention, irrespective of their protocol adherence and continued participation in the study.

Table 2 **Populations for Analysis**

Population/analysis set	Description
	
Participants who withdraw consent to participate in the study will be included up to the date of their study withdrawal. Participants will be classified according to the study intervention they actually received.
 
The SAF is to be used for safety analyses.

Immunogenicity analysis set (IAS)	
All participants in the SAF who have no important protocol deviations judged to have the potential to interfere with the generation or interpretation of an immune response and have baseline and at least one post-baseline immunogenicity samples collected. Participants will be classified according to the study intervention they actually received.
 
The IAS is to be used for the analysis of immunogenicity endpoints.

In addition to the analysis sets defined above, summaries of participant disposition and participants not randomized will be performed in a Screened set, including all participants who have provided informed consent.

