3.4 General Considerations

Data will be provided in data listings sorted by vaccination group and participant number. Tabular summaries will be presented by vaccination group and overall. Vaccination group will be defined as the actual vaccination received by a randomized participant.

Categorical variables will be summarized using frequency and percentages, where the denominator for calculation is the underlying analysis set population, unless otherwise stated. Continuous variables will be summarized with descriptive statistics of number of available observations, mean, standard deviation, median, minimum, maximum, and quartiles where appropriate.

All point estimates will be presented with a two-sided 95% CI, unless otherwise stated. For subgroup analyses, CIs will be presented for subgroup categories which have at least 5 evaluable participants per vaccination group.

The RSV nAb responses are measured as concentrations in IU/mL and therefore the geometric mean responses will be referred to as GMCs while the hMPV nAb responses are measured as titers (1/dilution) and the geometric mean responses will be referred to as GMTs. The GMCs and GMTs are referred to generally as geometric mean responses.

Immunogenicity summaries involving the Day 29 endpoint will include participants in the immunogenicity analysis set with a non-missing baseline and a non-missing result at Day 29.

For immunogenicity summaries involving data through Day 181, evaluable participants will be those in the immunogenicity analysis set with non-missing baseline and at least one non-missing post-baseline (Day 29 or 181) result.

Immunogenicity results below the LLoQ will be imputed to half of the LLoQ and results above the ULoQ will be imputed to the ULoQ prior to computing geometric mean responses. Responses will be imputed before any model-adjustment is performed.

The data analyses will be conducted using the SAS® System version 9.4 or above (SAS Institute Inc., Cary, NC). All SAS® programs used to generate analytical results will be developed and validated according to AstraZeneca programming standards and validation procedures.

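### Must the SAP state how the least square means weight the three age strata?

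*SAP*

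**What the plan says.** Table 4 in SAP 4.2 lists "Model-adjusted GMCs by vaccination group" among the summaries for the primary immunogenicity objective. Section 4.2.1.5 obtains them from an ANCOVA of log2 Day 29 response on study group, log2 baseline and a three-level age group, with no group-by-age term: "Least square means and 95% CIs will be back-transformed to provide Day 29 model-adjusted GMCs". Section 4.2.3.2 does the same from the MMRM: "Least square means and 95% CIs will be back-transformed to provide model-adjusted GMC/GMTs and confidence intervals by study group".

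Neither section gives weights for the age levels. SAP 3.4 names the software ("System version 9.4 or above") but no procedure or margins option, and Protocol 9.4.2.1 does not mention weights either. The population is set in SAP 3.3: "The IAS is to be used for the analysis of immunogenicity endpoints". On the strata, Protocol 6.3 says "Randomization will be centrally stratified by age"; no quota, cap or expected share is given for any of them.

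**The concern.** A least square mean from a model with a categorical covariate is an average over that covariate's levels, so its value depends on the weights. Many analysts would take the term to mean equal weights, one third per stratum here, but that is an inference and not SAP text. Stratified randomization balances the groups within strata; it does not make the strata the same size. If few participants aged 80 or over enrol, an equal-thirds mean leans heavily on a sparse stratum. Its interval is then wider, and the GMC describes an age mix that the immunogenicity analysis set does not have.

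The affected quantity is a summary for the primary objective, and two programmers could follow 4.2.1.5 faithfully and report different values. The planned bar and line plots also set raw baseline GMCs, which carry the observed age mix, beside adjusted Day 29 GMCs, which might not. Protocol 4.2 says the study should help refine Phase 3 assumptions, so the level has some use of its own.

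**Working it through.** **Inputs.** About 70 per group and two-sided 95% intervals (SAP 3.1, 3.4). The SD is redacted. The age mixes are my assumptions.

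**Reproducing the plan's own figure.** The CI is ratio ×/÷ 10^(1.96 × SD × √(4/N)). An SD of 0.60 log10 (1.99 log2), back-solved from Table 1, gives 1.96 × 0.60 × √(4/140) = 0.199, and 10^0.199 = 1.580. So 0.9/1.580 = 0.57 and 0.9 × 1.580 = 1.42, as stated in SAP 3.1. The same SD reproduces 23 of the 24 limits in Table 1; the exception is 1.348 against a printed 1.34. This shows that the table is consistent with one SD. It does not check that SD independently, and the ANCOVA residual SD may be smaller.

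**Effect on the between-group ratio.** In the additive model the adjusted mean for group g is μ + α_g + β·x̄ + Σ w_j γ_j, where w_j are the age weights. The difference between groups is α_1 − α_0, so the weights cancel. The MMRM has a group-by-visit term but no age interaction, so the same holds at Day 29 and at Day 181. At this SD the Day 29 ratio has a CI of ×/÷ 1.587 (t quantile) under either weighting.

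**Effect on the per-group level.** With groups balanced within strata, n_j per group in stratum j and the baseline covariate left out, Var = σ²[1/140 + Σ w_j²/(2n_j)].

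- Observed shares, w_j = n_j/70: Var = σ²(1/140 + 1/140) = σ²/70.
- Equal thirds: Var = σ²[1/140 + (1/18) Σ 1/n_j].

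Worked case, 35/25/10: Σ 1/n_j = 0.1686; 0.1686/18 + 1/140 = 0.01651; 70 × 0.01651 = 1.156; √1.156 = 1.075.

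In the table, the CI factor at SD 0.60 log10 uses t = 1.978. At observed shares it is 10^(1.978 × 0.60/√70) = 1.386 for every mix. The last column assumes a fall of 0.25 log2 per age band given baseline and equals 2^Σ(1/3 − n_j/70)d_j, with d = (0, −0.25, −0.50).

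| Assumed mix per group (60–69/70–79/80+) | SE ratio, equal to observed | CI factor, equal weights | Level, equal to observed |
|---|---|---|---|
| 24/23/23 | 1.000 | ×/÷ 1.386 | 0.998 |
| 28/25/17 | 1.012 | ×/÷ 1.391 | 0.973 |
| 32/24/14 | 1.030 | ×/÷ 1.400 | 0.956 |
| 35/25/10 | 1.075 | ×/÷ 1.421 | 0.940 |
| 39/24/7 | 1.148 | ×/÷ 1.455 | 0.924 |
| 45/21/4 | 1.321 | ×/÷ 1.539 | 0.903 |

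The SE ratio does not depend on the SD. With no age effect given baseline, the last column is 1.000 throughout. Even the largest shift shown (0.903) lies well inside the per-group interval at observed shares, 0.72 to 1.39 times the GMC.

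**With the baseline covariate, and in the MMRM.** Adding a simulated baseline hardly changes the ratio: at 35/28/7 it is 1.14 with or without it. In a two-visit MMRM with within-person correlation 0.5 to 0.8, the ratio is 1.11 to 1.13 at 35/28/7 and 1.26 to 1.31 at 49/17/4, against 1.14 and 1.33 in the ANCOVA.

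**The case for a change.** The strongest case for a change is that the weights touch a primary summary, no sensitivity analysis is planned, stating them costs a line, and fixing them before results are seen removes a post hoc choice. With groups balanced within strata, observed margins are never less precise for the level. All of that is true, and a statistician drafting the SAP afresh might well include it.

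It falls short of a reason to amend. Equal and observed weights answer different questions: one describes a standard age mix that does not depend on recruitment, the other the mix enrolled. Reasonable statisticians choose either. For the same reason the SE ratio is a like-for-like loss of precision only if age has no effect given baseline; otherwise the two estimates have different targets. Naming the immunogenicity analysis set says who is analysed, and an equal-weighted mean is still estimated from those participants.

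The plot argument is only partly met by observed margins. An adjusted Day 29 GMC at pooled margins and a pooled mean baseline still differs in kind from each group's raw baseline GMC. Nor would one sentence close the matter. The baseline-tertile models in SAP 4.2.1.8 also average over age, yet a pooled mean baseline would normally fall outside the outer tertiles, so the age weights and the baseline value would have to be specified separately there.

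**Conclusion.** No change is needed. The SAP leaves out a programming detail that analysts will settle by a recognised convention, and either convention gives sound adjusted GMCs. The cost of equal weights is nil with equal strata and about 1% to 3% in the SE of each log GMC under mild imbalance. It becomes noticeable only if the 80+ stratum is small: 15% at 7 of 70 and 32% at 4 of 70. This rests on an inferred equal-weight default and on age mixes that appear nowhere in the documents. Any shift in level also needs an age effect given baseline, which no document shows.

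The study is descriptive, with no hypothesis test. The precision table concerns the ratio, which the weights do not affect. Unadjusted GMCs, which carry the observed age mix, and GMCs by age group are already planned, so a reader who wants the level at the enrolled mix or within a stratum will have it. Naming the age weights in the table footnotes or programming specifications would be an optional courtesy.
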